9.2 Cosmesis

9.2.1 Patients who have breast mound reconstructions will have the type and timing of the reconstruction recorded. Need for reconstruction revisions will be recorded.

9.3 Collection and analysis of tumor and serum samples

Several candidate predictors of radiosensitivity or radioresistance have been explored, both at the molecular and genetic level, and our group is actively participating in these research efforts⁶¹.

predictors of host sensitivity and tumor sensitivity to radiation therapy.

◊ [REDACTED] from study IRB 0220070169 will be [REDACTED] relative science/translational studies.

[figure not shown]

10. Removal of Patients from Study/Off Study Criteria

In the absence of treatment delays due to adverse events, treatment may continue until one of the following criteria applies:

- a) Disease progression/relapse during active treatment,
- b) Intercurrent illness that prevents further administration of treatment,
- c) Unacceptable adverse event(s),
- d) In the event of any drug-related life-threatening toxicity or laboratory abnormality the patient will be withdrawn from further treatment,
- e) Patient decides to withdraw from the study,
- f) Noncompliance with treatment plan,
- g) General or specific changes in the patient's condition render the patient unacceptable for further treatment in the judgment of the investigator, or
- h) Protocol violation - any patient found to have entered this study in violation of the protocol might be discontinued from the study at the discretion of the Principal Investigator.

11. Laboratory Evaluation – Optional Correlative Studies and Future Use

[figure not shown]
[figure not shown]
12. Pharmaceutical / Devices Information

This is a radiation therapy study and no pharmaceutical agents or devices will be used.

[figure not shown]
13. Data Collection and Records to be Kept

13.1 Case Report Forms (CRFs)

The Principal Investigator will be responsible for assuring that all data specified in the study-specific data capture plan is collected and entered onto the electronic case report forms (eCRFs).

13.2 Research Charts

13.3 Reports

Publications and annual reports for submission to the [REDACTED] will be initiated by the CRU PI using the data captured on the CRFs.

14. Data and Safety Monitoring

[REDACTED]

15. Multi-Institutional Guidelines (e.g., CINJ Oncology Group trials)

15.1 IRB Approvals

[REDACTED]

15.2 Other Pre-Study Documents

Each participating center is required to have the following documents on file at CINJ OHRS:

- Curricula Vitae of all Physician Investigators
- [REDACTED]
- [REDACTED]
- Signed Investigator agreement from the Principal Investigator at each participating center
- Medical license from each Investigator

15.3 Initiation Meetings

A study initiation meeting will be conducted with each participating institution prior to enrollment of patients from the institution. OHRS staff will conduct the study initiation meeting in close proximity to IRB approval of the study at the participating center. In most situations the study initiation meeting will be conducted via teleconference. Web-based training regarding e-CRF completion will be utilized as appropriate.

15.4 IRB Continuing Approvals

[REDACTED]

15.5 Amendments and Consents

[REDACTED]

15.6 Patient Registration

All patients from participating institutions must register patients with the OHRS central registration desk, as described in Section 5.7 of this protocol.

15.7 Data Collection and Toxicity Reporting

The PI at each institution will be responsible for assuring that all the required data is collected and entered onto the eCRFs accurately and completed eCRFs submitted as described in Section 13.

15.8 Data Monitoring and Source Document Verification

[REDACTED]

15.9 Data and Center Audits

[REDACTED]

16. Statistical Considerations

16.1 Primary and Secondary Hypotheses

The primary hypothesis of this study is that the delivery of hypofractionated, accelerated chest wall radiotherapy will result in toxicities will be similar to those reported for this patient population using standard of care postmastectomy radiation therapy.

The secondary endpoint is that locoregional control that is equal (non-inferior) to that reported for a conventional fractionation course of postmastectomy radiotherapy.

16.2 Sample Size Justification

The primary aim of this study is to ensure that the toxicity rate (defined as chest wall pain greater than or equal to grade 3, or painful/symptomatic brachial plexopathy and acute symptomatic pneumonitis greater than or equal to grade 3) from hypofractionated post-mastectomy radiation is controlled at an acceptable level. The current toxicity rate from standard regimens is approximately 3%. We need to ensure that the rate from the hypofractionated scheme is as low as possible, and specifically that it is below 9% with 80% power, using a 10% level one-sided test of proportions. To meet this requirement, we will need to accrue 67 patients. If there are 5 or more toxicity events among 67 patients, we reject the hypothesis that the rate is 3%. The exact significance level of this discrete variable test is 0.0508, and the exact power is 0.732.

Early stopping: The study will be stopped early if, at any time, we are more than 80% sure that the toxicity rate exceeds 9%. For example, if we have 4 patients experiencing a toxicity event out of the first 33 patients enrolled, we will stop the trial. But if there are only 3 patients with toxicity, the trial would continue. As mentioned above, if five patients show unacceptable toxicities, the trial will end, even if this happens before the full 67 patients have been accrued. This stopping rule table consists of posterior probabilities that the true toxicity level exceeds 9%, assuming a uniform prior on a binomial distribution.

		k: Number of unacceptable toxicities				
		0	1	2	3	4
1	0.8281	0.9919				
2	0.753571	0.977158	0.999271			
3	0.68575	0.957035	0.997281	0.999934		
4	0.624032	0.932619	0.993659	0.999696	0.999994	
5	0.567869	0.904847	0.988165	0.999152	0.999967	
6	0.516761	0.874519	0.980667	0.998463	0.999894	
7	0.470253	0.84232	0.971113	0.996589	0.999738	
8	0.42793	0.808834	0.959522	0.994296	0.999455	
9	0.389416	0.774553	0.94596	0.991166	0.99899	
10	0.354369	0.739891	0.930533	0.987098	0.998286	
11	0.322475	0.705194	0.915376	0.982007	0.997279	
12	0.293453	0.670749	0.894639	0.97583	0.995905	
13	0.267042	0.636792	0.874489	0.968523	0.994098	
14	0.243008	0.603515	0.853096	0.96006	0.991796	
15	0.221137	0.571069	0.830634	0.950433	0.98894	
16	0.201235	0.539575	0.807273	0.939651	0.985474	
17	0.183124	0.509125	0.78318	0.927737	0.98135	
18	0.166643	0.479785	0.758515	0.914727	0.976525	
19	0.151645	0.451602	0.73343	0.900668	0.970963	
20	0.137997	0.424606	0.708065	0.885617	0.964637	
21	0.125577	0.398811	0.682554	0.869637	0.957525	
22	0.114275	0.37422	0.657017	0.852799	0.949615	
23	0.10399	0.350825	0.631565	0.835179	0.940902	
24	0.094631	0.32861	0.606299	0.816854	0.931387	
25	0.086114	0.307552	0.581307	0.797904	0.921079	
26	0.078364	0.287622	0.556669	0.77841	0.909993	
27	0.071311	0.268789	0.532454	0.758453	0.89815	
28	0.064893	0.251016	0.508725	0.738113	0.885578	
29	0.059053	0.234265	0.485531	0.717468	0.872306	
30	0.053738	0.218496	0.462917	0.696594	0.858371	
31	0.048902	0.203668	0.440919	0.675563	0.843811	
32	0.044501	0.189739	0.419566	0.654445	0.828668	
33	0.040496	0.176667	0.398882	0.633306	0.812988	
34	0.036851	0.164412	0.378883	0.612208	0.796817	
35	0.033534	0.152931	0.35958	0.591209	0.780202	

We will use a fixed sample size of 67 patients, with locoregional recurrence rate as the secondary outcome of interest. For up to 5 recurrences out of 67 patients, we can say with 90% confidence that the true recurrence rate would be between 3.7% and 14.5%. We feel this is an acceptable level, and would be deemed non-inferior to previously reported recurrence rates.

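### Section 16.2 joins brachial plexopathy and pneumonitis with *and*, so read literally either one alone, without grade 3 or higher chest wall pain, is not a primary toxicity event

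*Combined protocol and SAP*

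**What the plan says.** Section 16.2 gives the only readable definition of the event behind the primary aim. It has two limbs. The first is chest wall pain of at least grade 3. The second reads: "or painful/symptomatic brachial plexopathy and acute symptomatic pneumonitis greater than or equal to grade 3".

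The design figures follow in the same section:
- The rate on standard regimens is put at about 3%, and the aim is to show that "it is below 9% with 80% power, using a 10% level one-sided test of proportions".
- The sample size is 67. The decision rule is: "If there are 5 or more toxicity events among 67 patients, we reject the hypothesis that the rate is 3" per cent.
- "The exact significance level of this discrete variable test is 0.0508, and the exact power is 0.732".
- The trial stops early if the posterior probability that the rate exceeds 9% is above 80% under a uniform prior. Separately, "if five patients show unacceptable toxicities, the trial will end". The term in that last sentence is not defined on its own.

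Elsewhere the toxicities appear without a composite. Section 9.1.2 asks for plexopathy and pain to be recorded at each visit and does not list pneumonitis. CRF #2 in Appendix D has separate lines for brachial plexopathy, acute lung toxicity and pain. Section 16.4 says only that toxicity is collected as dichotomous variables.

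**The concern.** The definition has a comma and *or* after chest wall pain, then *and* between the other two toxicities. Taken as written, the event is: pain of grade 3 or higher, OR (plexopathy AND pneumonitis). Pain qualifies by itself. Plexopathy or pneumonitis qualifies only if the other is also present, or if the patient has qualifying pain anyway. If plexopathy and pneumonitis seldom occur in the same patient, the composite is close to chest wall pain alone.

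The same phrase has a second ambiguity. The closing grade threshold may govern pneumonitis only, or plexopathy as well. The plexopathy section of CRF #4 records onset, detection, symptoms and treatment, but no grade, so it could not supply one.

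The parenthesis determines what is counted against the cut-off of 5 and against the stopping table. With so low a cut-off, one or two disputed patients can change the conclusion. Section 15 provides for several participating centers, so different people may classify events. Settling the meaning after events have occurred would be a post hoc decision on the primary outcome.

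**Working it through.** **Inputs from Section 16.2:** n = 67; cut-off 5; null rate 3%; unacceptable rate 9%; posterior threshold 0.80 with a uniform prior. **Not in the documents:** the separate rates of the three toxicities and their overlap. These are assumed below.

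**1. Reproduce the plan's figures.** The chance of 5 or more events is 1 − Σ C(67,k) p^k (1−p)^(67−k), k = 0 to 4.
- p = 0.03: 1 − (0.1299 + 0.2692 + 0.2748 + 0.1841 + 0.0911) = 1 − 0.9492 = 0.0508, as stated.
- p = 0.09: 1 − (0.0018 + 0.0119 + 0.0390 + 0.0835 + 0.1322) = 1 − 0.2684 = 0.7316, stated as 0.732.
- Stopping table: the posterior is Beta(1+k, n−k+1). P(rate > 0.09) is 0.8130 for 4 of 33 and 0.6333 for 3 of 33. Both match the table.

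No printed figure is wrong because of the wording. The question is which patients enter the count.

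**2. Rate counted under the literal reading.** Suppose the true any-of-three rate is 9%. With negligible overlap, the literal rule counts only the share of events due to pain.

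| Assumed share due to pain | Rate counted | P(5 or more of 67) | P(4 or more of first 33) |
|---|---|---|---|
| Any one counts (no loss) | 9% | 0.732 | 0.346 |
| Two thirds | 9% × 2/3 = 6% | 0.375 | 0.134 |
| One third (equal split) | 9% × 1/3 = 3% | 0.051 | 0.017 |

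For 6%: 1 − (0.0158 + 0.0677 + 0.1426 + 0.1973 + 0.2015) = 1 − 0.6249 = 0.375. The last column is a single look at 33 patients, not the full sequential rule.

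**3. Sensitivity to overlap and split.** Let the components be independent, with an any-of-three rate of 9%. A component with share w then has rate 1 − 0.91^w, and the counted rate is 1 − (1 − p_pain)(1 − p_plex × p_pneu).

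| Pain / plexopathy / pneumonitis | Component rates | Rate counted | P(5 or more of 67) |
|---|---|---|---|
| 60 / 20 / 20 | 5.5%, 1.87%, 1.87% | 5.5% | 0.313 |
| Equal | 3.09% each | 3.2% | 0.063 |
| 20 / 40 / 40 | 1.87%, 3.7%, 3.7% | 2.0% | 0.011 |

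Under every split tried, the literal reading makes it harder to detect excess toxicity. The size of the loss varies widely with the split.

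**4. Does any other section settle the reading?** Sections 9.1.2 and 16.4 and CRF #2 record or mention the toxicities but define no composite. Section 16.1 speaks of toxicities in general. None says that one of the three suffices.

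**The case against.** The strongest reply is that nobody would apply the literal reading. Section 16.2 is listing the toxicities that make up a rate, and in such a list *and* can be loose wording for *any of*. Requiring both toxicities in one patient would be an odd design, and CRF #2 treats them as separate items to be evaluated at every visit. This largely stands: *any of* is probably what was meant, and nothing shows that the sponsor chose a conjunctive endpoint. What remains is that the text does not say so, and the text is what controls the count.

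A reader might infer that severe pneumonitis or plexopathy could neither stop this trial nor be noticed. The documents do not support that. Section 14, on data and safety monitoring, is redacted, so other trial-level review cannot be excluded. Serious adverse events have their own provisions in Section 8, and Sections 7.10.5 and 10 deal with toxicity in individual patients. The point concerns only the counting rule in 16.2.

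A reader might also take 5% as the actual power of the trial. It is not. It follows from an assumed equal split, which puts the counted rate exactly at the 3% null and so returns the stated significance level. Other splits give different answers, and the loss occurs only if the literal reading is used.

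Finally, a patient with isolated plexopathy or pneumonitis is still an event if she also has chest wall pain of grade 3 or higher.

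**Conclusion.** The point holds as an ambiguity in the primary event definition that should be removed. Read literally, Section 16.2 leaves out patients who have only plexopathy or only pneumonitis and no qualifying pain, from both the 5-of-67 test and the stopping table. No readable section corrects this.

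The size is conditional on the literal reading being applied, on a true any-of-three rate of 9%, and on assumed component shares. With negligible overlap, the chance of reaching 5 events falls from 0.73 to 0.375 (pain two thirds of events) or about 0.05 (equal shares). With independent components, the splits tried give 0.011 to 0.313. The stated significance level and power reproduce. They apply to an any-of-three event provided that 3% and 9% are rates for that composite, which Section 16.2 does not confirm.

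**What to change.** In Section 16.2, state that an event is a patient with at least one of the three toxicities, each patient counted once. Use that definition for the final test, the posterior stopping table and the five-patient stopping sentence, so that the term used there for unacceptable toxicity has the same meaning.

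The sponsor should settle two further points in the same place:
- whether the grade 3 threshold applies to brachial plexopathy;
- whether the 3% and 9% rates refer to the any-of-three composite.

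The cost is a sentence or two. If the rates do refer to this composite, the sample size, the cut-off and the stopping table do not change; if not, the design figures need to be revisited. If plexopathy is to be graded, CRF #4 needs a grade field. It is also worth checking where acute pneumonitis is graded: CRF #2 sends acute lung toxicity to CRF #3, whose readable respiratory rows are bronchospasm, cough, dyspnea and voice changes, while pneumonitis grades appear on the late-toxicity form, CRF #6.

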16.5 Statistical Analysis

All time intervals will be calculated from the date of diagnosis. Fisher's exact test will be performed to correlate clinicopathological covariates with toxicity and with plastic surgical revision. The association of variables with LR failure times will be investigated by fitting a parametric model and examining the significance of the parameter estimates. Nonparametric estimates of the survival or recurrence-free distributions or recurrence (failure) distribution will be obtained by life table methods. Tests will be declared statistically significant if the calculated P-value was ≤ 0.05 . All tests appear as 2-sided P-values.

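### Section 16.2 says 67 patients give 80% power at a one-sided 10% level; neither the final test nor the design with its stopping rule meets both, and not rejecting 3% does not show a rate below 9%

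*Combined protocol and SAP*

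**What the plan says.** Section 16.2 takes a reference rate for the composite toxicity endpoint: "The current toxicity rate from standard regimens is approximately 3" per cent. It wants assurance about the new schedule's rate, "specifically that it is below 9% with 80% power, using a 10% level one-sided test of proportions". It continues: "To meet this requirement, we will need to accrue 67 patients". The decision rule follows: "If there are 5 or more toxicity events among 67 patients, we reject the hypothesis that the rate is 3" per cent. The next sentence reports: "The exact significance level of this discrete variable test is 0.0508, and the exact power is 0.732".

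The same section adds a Bayesian rule with a uniform prior: "The study will be stopped early if, at any time, we are more than 80% sure that the toxicity rate exceeds 9" per cent. A table of posterior probabilities starts at patient 1. The worked example stops at 4 events in the first 33 patients and continues at 3. A fifth event ends the trial whenever it occurs.

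Section 16.1 words the primary hypothesis differently: toxicities "will be similar to those reported for this patient population" under standard treatment. Section 16.5 sets significance at 0.05 and adds: "All tests appear as 2-sided P-values".

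**The concern.** Three things do not fit together.

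- The section sets a power target, says 67 patients reach it, and then prints a power below it.
- The printed level and power belong to the final test alone. The trial as described can also stop on the posterior rule, and no error rate is given with that rule included.
- The hypothesis tested is a rate of 3%, while the aim is to show a rate below 9%. Failing to reject the first does not establish the second, and the plan does not say what 0 to 4 events will be taken to mean.

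This is the primary endpoint and the only sample-size justification. A schedule no more toxic than standard could be stopped far more often than the stated 5%, and a completed trial could claim a safety result that its data do not support.

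**Working it through.** **Inputs (all Section 16.2).** Null rate 3%, alternative 9%, one-sided level 10%, power 80%, n = 67, reject at 5 or more events; stop when the posterior probability of a rate above 9% exceeds 0.80; uniform prior; stop at the fifth event.

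**1. The plan's own figures.** With X binomial (67, p):

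- P(X ≥ 5 | 0.03) = 0.0508
- P(X ≥ 5 | 0.09) = 0.7316

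Both printed values reproduce. The sample size follows from the arcsine approximation, n = [(z0.90 + z0.80) / (2(asin√0.09 − asin√0.03))]² = [(1.2816 + 0.8416) / 0.2612]² = 66.06, rounded up to 67.

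**2. Other cut-offs at 67.** P(X ≥ 4) is 0.1419 at 3% and 0.8638 at 9%. A cut-off of 4 misses the level and a cut-off of 5 misses the power. Lower cut-offs raise the level further, and higher ones lower the power further.

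**3. Adding the stopping rule.** After n patients with k events the posterior is Beta(k+1, n−k+1). Its tail above 0.09 reproduces the printed table and crosses 0.80 as follows:

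| Events | Last patient at which the rule stops | Posterior probability |
|---|---|---|
| 1 | 8 | 0.8088 |
| 2 | 16 | 0.8073 |
| 3 | 24 | 0.8169 |
| 4 | 33 | 0.8130 |

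The cell for 0 events in 1 patient (0.8281) also exceeds 0.80. It is left out, because applying it would stop every trial at the first patient.

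An exact patient-by-patient recursion to n = 67, with these boundaries and the five-event stop, gives the chance of stopping or rejecting:

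| Posterior rule active from | True 3% | True 9% | True 9% passes |
|---|---|---|---|
| 1st event | 25.8% | 83.6% | 16.4% |
| 2nd event | 11.9% | 78.3% | 21.7% |
| 3rd event | 7.2% | 75.4% | 24.6% |
| 4th event | 5.6% | 73.9% | 26.1% |
| Final test alone | 5.1% | 73.2% | 26.8% |

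The target is at most 10% and at least 80%. A wider search varied the first look (patient 1 to 67), the spacing of looks (1 to 34), the minimum event count (1 to 4) and whether the five-event stop applies. No version met both; the best power with the level held to 10% was 77.0%.

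**4. What a passing result shows.** The exact one-sided 90% upper bound is the p that solves P(X ≤ x | n, p) = 0.10:

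- 2/67: 7.7%
- 3/67: 9.7%
- 4/67: 11.6%

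Only 2 or fewer events exclude 9% at the 10% level.

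**The case against.** The power shortfall is disclosed. The plan sized the trial by a recognised approximation and then printed the exact values, so 67 is not a slip in the sums and a reader can see 0.732. That stands as an explanation. It does not withdraw the statement that 67 patients meet the requirement.

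The 25.8% is the extreme case. It needs a stop on a single event within the first 8 patients, with each outcome known before the next enrolment. The composite includes brachial plexopathy, which Section 9.1.2 records at follow-up visits, so some events will come late. Suppose enrolled patients form the denominator and events are known L patients late (an assumption). The first-event figures at true 3%/9% then become 21.5%/81.6% for L = 2, 16.9%/79.5% for L = 4, 12.1%/77.3% for L = 6 and 7.0%/74.8% for L = 8. The only worked example, 4 in 33, gives 5.6%/73.9%, close to the printed values. So 25.8% should be read as the upper end of a range. Still, the rule is said to apply at any time, the table starts at patient 1, and none of the lagged versions meets both targets. Counting a safety stop together with a rejection is a convention, but either one ends the trial against the schedule.

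Setting an acceptable rate against an unacceptable one is ordinary phase II practice, and 5 events is a usable rule. What is missing is the meaning of 0 to 4 events. The 90% bound is one choice of criterion, taken here to match the plan's own 10% level.

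On Section 16.5, the specific one-sided 10% test can reasonably be read as overriding the general statement. That point is minor.

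**Conclusion.** The concern holds. The exact power of the final test is 73.2%, which is 6.8 points below the 80% claimed, and no cut-off at 67 patients meets both targets. The error rates of the design with its stopping rule are not reported. Depending on when the rule becomes active, the false-alarm rate at a true 3% lies between 5.6% and 25.8%, and no version examined meets 10% and 80% together. That range assumes outcomes known in sequence and leaves out the cell for 0 events in 1 patient. The power shortfall and the inference point need neither assumption. With 3 or 4 events the trial passes its test while 9% remains inside the one-sided 90% bound, so the stated aim is not shown.

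**What to change.** In Section 16.2:

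- Delete the statement that 67 patients meet 80% power at the 10% level.
- Label the exact 5.1% and 73.2% as describing the final test alone, without early stopping.
- State how the posterior rule will be applied: from which event or patient, and with what follow-up before a patient counts. Give the level and power of the full design on that basis.
- Report the exact one-sided 90% upper bound with the primary result. Describe the rate as below 9% only if the bound is under 9% (2 or fewer events in 67). Say that 3 or 4 events mean only that 3% was not rejected, and align Section 16.1 with this.

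In Section 16.5, exempt the one-sided primary test from the two-sided 0.05 criterion.

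This costs text and one short calculation, with no added patients. The price is candour: at a true 3% the trial could claim a rate below 9% with probability P(X ≤ 2) = 67.4%, or 57.6% if the stopping rule acts from the first event, and 3 or 4 events would support neither conclusion.

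If the 10%/80% target is to be kept, the smallest exact size for the 3% null is 74 patients (5 or more events: 7.2%/80.7%), 7 more than planned. With the stopping rule it still meets the target from the third event (9.0%/82.0%) or fourth (7.6%/81.0%), but not from the first (27.0%/87.6%) or second (13.4%/83.9%). At 74, 3 events have an upper bound of 8.8%, but 4 events have 10.5%, so the wording for 4 events would still be needed. If the test is instead turned round to reject a rate of 9% or more, 73 patients with 3 or fewer events give a level of 9.6% and power of 82.4% at a true 3%, before any posterior stopping.

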4.1 Duration of Study

Patients will be enrolled in this trial over the course of approximately 36 months. The duration of the protocol for each patient will be from the date of registration to the last day of radiation therapy. Patients will be followed regularly after treatment as per standard departmental policy (Section 9.2.1). The duration of the study is estimated to be 72 months, such that the minimum follow-up in the study cohort is 36 months.

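### The early-stopping rule is met by zero toxicities in one patient, and the plan reports no error rates for it: checked after every patient, it stops a true 3% regimen 25.8% of the time, while 0.0508 and 0.732 describe only the fixed 5-of-67 test

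*Combined protocol and SAP*

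**What the plan says.** Section 16.2 sets the reference rate: "The current toxicity rate from standard regimens is approximately 3" per cent. The new schedule's rate is to be shown to be "specifically that it is below 9% with 80% power, using a 10% level one-sided test of proportions". With 67 patients, five or more events reject 3%, and the plan adds: "The exact significance level of this discrete variable test is 0.0508, and the exact power is 0.732".

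A separate early-stopping paragraph follows: "The study will be stopped early if, at any time, we are more than 80% sure that the toxicity rate exceeds 9" per cent. The worked example stops on "4 patients experiencing a toxicity event out of the first 33 patients enrolled" and continues on three. A fifth event ends the trial whenever it occurs. The accompanying table gives the posterior probability that the rate exceeds 9%, "assuming a uniform prior on a binomial distribution". It runs from n = 1 to n = 35, and its first cell (one patient, no toxicity) reads 0.8281.

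Section 16.2 gives no minimum number of patients, no exception for zero events, and no stopping probability or expected enrolment for the combined rule. Section 14 (Data and Safety Monitoring) is redacted.

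**The concern.** The rule and its table conflict in the first row: 0.8281 is above 80%, so a first patient without toxicity would stop the trial. Nobody would act on that cell, but it has the same cause as a result that would be acted on. The prior starts far above the rates the trial hopes to see, so one event in the first eight patients crosses the threshold.

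The only error rates in the plan belong to the fixed test. A reader may take 5.08% and 73.2% as properties of the whole trial. Under the rule as written, a regimen exactly as toxic as the plan's 3% standard can be halted far more often than 5.08%, and more often than the 10% level chosen for the final test. Section 16.2 calls control of this toxicity rate the primary aim, so the chance of ending the trial wrongly on it should be known beforehand.

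**Working it through.** **Inputs, all from section 16.2.** Reference rate 3%; unacceptable rate 9%; N = 67; rejection at 5 or more events; posterior threshold 0.80 with a uniform prior; stop at the fifth event. Accrual over about 36 months comes from section 4.1.

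**1. The plan's own error rates.** Exact binomial tails: P(X ≥ 5 | 67, 0.03) = 0.0508 and P(X ≥ 5 | 67, 0.09) = 0.7316. Both stated figures reproduce. Stopping at the fifth event does not change them.

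**2. The posterior table.** With a uniform prior, the posterior after k events in n patients is Beta(k + 1, n − k + 1).
- Before any data, P(rate > 9%) = 1 − 0.09 = 0.91.
- n = 1, k = 0: 0.91² = 0.8281, as printed and above 0.80.
- n = 2, k = 0: 0.91³ = 0.7536, so only the first zero-event cell crosses.
- k = 1: 0.977 at n = 2, falling to 0.809 at n = 8, then 0.775 at n = 9.

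Two printed cells differ slightly from the formula: n = 6, k = 3 (0.998463 printed, 0.998163 computed) and n = 11, k = 2 (0.915376 printed, 0.913376 computed). Neither affects stopping.

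**3. The implied boundary** (fewest events that stop the trial, zero-event cell left out):

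| Patients | Events to stop |
|---|---|
| 1–8 | 1 |
| 9–16 | 2 |
| 17–24 | 3 |
| 25–33 | 4 |
| 34–67 | 5 |

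From n = 43 five events no longer give a posterior above 0.80, and only the five-event cap acts.

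**4. Combined rule at a true 3%, checked after every patient, outcomes known at once.** Exact forward recursion: q(n, k) = 0.97·q(n − 1, k) + 0.03·q(n − 1, k − 1), removing mass that reaches the boundary.
- Patients 1–8: 1 − 0.97⁸ = 0.2163.
- Patients 9–16: 0.97⁸ × P(2 or more of 8) = 0.78374 × (1 − 0.78374 − 0.19392) = 0.0175.
- Patients 17–33: 0.0059.
- Patients 34–67: 0.0185.
- Sum: 0.2582.

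The same recursion at 9% gives 0.8356. If the zero-event cell is applied literally, every trial stops after one patient, because both n = 1 cells (0.8281 and 0.9919) exceed 0.80.

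**5. Dependence on the first look:**

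| First look at patient | P(stop), true 3% | P(stop), true 9% | Expected enrolment, true 3% |
|---|---|---|---|
| 1 | 25.8% | 83.6% | 52.1 |
| 9 | 11.9% | 78.3% | 61.8 |
| 17 | 7.2% | 75.4% | 64.9 |
| 25 or 33 | 5.6% | 73.9% | 66.0 |
| Five-event cap only | 5.08% | 73.2% | 66.3 |

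Looks every 5 patients give 19.9% at 3%; every 10 patients, 8.3%.

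**6. Dependence on delayed events.** The documents give no delay to onset, so this is an assumption: a fixed delay, even accrual of 67 patients over 36 months, a check whenever an event surfaces, and n counting everyone enrolled by then. Simulation (200,000 trials) at a true 3% gives about 23.7% for a 1-month delay, 19.2% for 2 months, 14.5% for 3, 5.9% for 6 and 5.1% for 12.

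**The case against.** The case against the concern does not dispute the arithmetic; it is about weight.

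- **25.8% is the upper end of the range.** It assumes a check after every patient and immediate outcomes. Section 9.1.1 schedules the first post-treatment visit 2–8 weeks after radiotherapy, and radiotherapy lasts 15–19 days (section 7.6). That visit therefore falls 15 + 14 = 29 to 19 + 56 = 75 days after the start. Delays of 1 and 2.5 months give roughly 24% and 17% if n counts enrolled patients. This stands as a reason to report a range. It does not remove the problem: continuous checking is what the rule says, and 25.8% applies if n counts only assessed patients.
- **A safety stop is not a type I error.** This is correct. The 10% level belongs to the final test, the plan attaches 0.0508 to that test, and an early stop is not declared a rejection of 3%. Both sets of figures are therefore needed, and neither replaces the other.
- **The missing choices are partly stated.** The wording on timing implies continuous looks, the example counts enrolled patients, and section 8 makes anyone given one dose evaluable for toxicity. None of this says how patients still awaiting assessment count at an interim check. Section 14 is redacted and may hold procedures, but they would have to agree with section 16.2.
- **Caution early in a trial is defensible, and the zero-event cell is a drafting slip.** Both are fair. The first is a choice the sponsor can make only with the figures in view; the second still needs correcting because the printed rule gives a wrong result.

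**Conclusion.** The concern holds. As printed, the rule is met with no toxicity in one patient. With that cell set aside, the combined rule stops a true 3% regimen between about 5% and 26% of the time, depending on the first look, the denominator and how soon events surface. The rule taken at its word, with immediate outcomes, gives the top of that range: 25.8% at 3% and 83.6% at 9%. Of the 25.8 points, 21.6 come from one event in the first eight patients. The figures 0.0508 and 0.732 are right for the fixed test and should not be read as properties of the trial. The exact results rest on independent patients with a common toxicity rate; the delay results also rest on the assumed fixed delay and even accrual. The missing first look and denominator would on their own be only a gap in detail.

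**What to change.** 1. Remove the stop at one patient with no toxicity, for example by stating that the posterior rule applies only once at least one toxicity has occurred.
2. Beside 0.0508 and 0.732, report the exact probability of stopping at 3% and 9% for the combined rule. If the table is kept with a check after every patient, these are 25.8% and 83.6% with immediate outcomes. Say that an early stop is a safety decision and not a rejection of 3%.
3. State when the first look occurs and whether n counts patients enrolled or patients whose toxicity has been assessed.

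If the sponsor finds the false-stop rate too high, it may recalibrate the prior or the first look. That choice is the sponsor's, and the price is slower stopping when toxicity is high. Expected enrolment at a true 15% rate is 11.2 with a check after every patient, 18.7 from patient 9 and 25.3 from patient 17; at a true 30% rate it is 3.6, 9.8 and 14.7.

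The cost is a few lines, a short table of operating characteristics and a less favourable stated error rate. No extra patients are needed.
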